**Table 2. Varenicline reminders**

Pre-Quit Day 1 Message	Don't forget to take your Chantix pill tonight!		
Pre-Quit Days 2-3 Message	Don't forget to take your Chantix pill this morning!		
Pre-Quit Day 4-7	Don't forget to take your Chantix pill twice daily (morning and night)!		
Day 8 to end of treatment	Don't forget to take your Chantix pill twice daily (morning and night)!		
AM		PM	
Reminder 1 (30 minutes after Daily Diary)	You were scheduled to take your morning Chantix pill at [INSERT TIME] AM. Have you taken your Chantix pill this morning? (Yes/No)	Reminder 1 (2 hours and 30 minutes after before sleep time)	You were scheduled to take your evening Chantix pill at [INSERT TIME] PM. Have you taken your Chantix pill this morning? (Yes/No)
Reminder 2 (1 hour after Reminder 1)	You were scheduled to take your morning Chantix pill at [INSERT TIME] AM. Have you taken your Chantix pill this morning? (Yes/No)	Reminder 2 (1 hour after Reminder 1)	You were scheduled to take your evening Chantix pill at [INSERT TIME] PM. Have you taken your Chantix pill this morning? (Yes/No)
Reminder 3 (1 hour after Reminder 2)	You were scheduled to take your morning Chantix pill at [INSERT TIME] AM. Have you taken your Chantix pill this morning? (Yes/No)	Reminder 3 (1 hour after Reminder 2)	You were scheduled to take your evening Chantix pill at [INSERT TIME] PM. Have you taken your Chantix pill this morning? (Yes/No)

	
If no: What are the main reasons that you did not take your Chantix pill this morning? (Check all that apply)
 
 
1. I forgot to take it.
 
2. I was away from home.
 
3. I experienced side effects.
 
4. I didn't feel like I needed it.
 
5. I didn't think it is working.
 
6. I have decided not to quit smoking.
 
7. Other
 
		
If no: What are the main reasons that you did not take your Chantix pill this evening? (Check all that apply)
 
 
1. I forgot to take it.
 
2. I was away from home.
 
3. I experienced side effects.
 
4. I didn't feel like I needed it.
 
5. I didn't think it is working.
 
6. I have decided not to quit smoking.
 
7. Other
 

--	--	--	--

NRT Reminder. Participant will receive a message and then be asked if they have used NRT in the past 2, 4, or 8 hours.

Quit Day – 4 Weeks Post-Quit: Reminder every 3 hours

5 Weeks Post-Quit – 8 Weeks Post-Quit: Reminder every 4 hours

9 Weeks Post-Quit – 12 Weeks Post-Quit: Reminder every 6 hours

[figure not shown]

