Additional supply of gum or lozenges will be provided during in-person visits or through the mail. Participants assigned to VAR+N with medication reminders will receive smartphone prompts (through the Insight™ app) (during waking hours) reminding them to use a piece of gum or a

lozenge every 3 hours through 4 weeks post-quit, every 4 hours during post-quit weeks 5-8, and every 6 hours during post-quit weeks 12.

Reminders. Participants assigned to the reminder groups will receive reminders to take varenicline and/or oral NRT as follows:

Varenicline Reminders. Participants will receive varenicline reminders that correspond with the medication schedule. The reminders will provide a message and then ask the participant if they have taken medication. Reminder 2 will only appear if the participant has reported “no” to reminder 1. Reminder 3 will only appear if the participant has reported “no” to reminder 2. On the 3rd reminder the participant will be asked why they did not take their medication.

Pre-Quit Day 1: Only PM reminder (1 white pill (0.5 mg) daily)

Pre-Quit Days 2-3: Only AM reminder (1 white pill (0.5 mg) daily)

Pre-Quit Days 4-7: AM and PM reminders (1 white pill (0.5 mg) in the morning and 1 in the evening)

Day 8 to end of treatment: AM and PM Reminders (1 blue pill (1 mg) in the morning and 1 in the evening)

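### Table 2: the three evening varenicline reminders ask about the morning pill, and the answer decides whether further evening prompts appear

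*Combined protocol and SAP*

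**What the plan says.** Table 2 sets out the varenicline reminders in an AM and a PM column, with three reminders in each. All three PM cells carry the same text: "You were scheduled to take your evening Chantix pill at [INSERT TIME] PM. Have you taken your Chantix pill this morning? (Yes/No". The question is word for word the one in the AM column, where it fits its opening sentence. When the third PM reminder is answered negatively, the participant is asked "What are the main reasons that you did not take your Chantix pill this evening".

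The Varenicline Reminders text in Section C makes the sequence depend on the replies: "Reminder 2 will only appear if the participant has reported “no” to reminder 1", and "Reminder 3 will only appear if the participant has reported “no” to reminder 2". The reason question comes with the third reminder.

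The same text gives the schedule. The first day is "Pre-Quit Day 1: Only PM reminder (1 white pill (0.5 mg) daily", and the next two are "Pre-Quit Days 2-3: Only AM reminder (1 white pill (0.5 mg) daily". From Day 4 to the end of treatment, both AM and PM reminders are sent.

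The time of the first PM prompt is given in Table 2 as "Reminder 1 (2 hours and 30 minutes after before sleep time".

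**The concern.** The PM column contradicts itself: the opening sentence and the reason item concern the evening pill, while the question between them concerns the morning. This is more than a slip in background text, because it is wording that participants see and because the reply controls what they see next. On a twice-daily day, a participant who took the morning pill and missed the evening one can truthfully answer yes, and the follow-up prompts then stop in the very case they exist for.

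Reminders versus no reminders is one of the two randomized factors, and Aim 2 tests its effect on adherence and cessation. At stake are whether the evening part of that intervention is delivered as intended, and whether the evening replies and missed-dose reasons can be interpreted. The plan gives no other PM wording that would settle the matter. A copying error from the AM column is the likely cause. A text-extraction fault is unlikely, since the same words stand in three cells while the PM reason item is intact.

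**Working it through.** No sample size, power or error-rate figure is involved, and the plan states no figure to reproduce. The check is a count of days and a walk through the branching rule.

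**Days on which the PM item is scheduled**

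- Treatment length (Section C, Study Design): 1 titration week + 12 weeks = 13 weeks; 13 × 7 = 91 days. The Smartphones paragraph also gives a 13-week medication period.
- Day 1: PM reminder only, 1 day.
- Days 2-3: AM reminder only, 0 PM days.
- Days 4-7: AM and PM, 4 days.
- Days 8-91: AM and PM, 91 − 7 = 84 days.
- Total PM days: 1 + 4 + 84 = 89, of which 88 also have a morning pill.
- Share of treatment days: 89 / 91 = 97.8%.

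This is a maximum per participant in the reminder groups. It falls if varenicline or the reminders are stopped, as Section C allows under Discontinuing Reminders, Varenicline, or NRT.

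**Branching on a twice-daily day, if the question is answered as worded**

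Pill status is taken at the time the prompt fires.

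| Morning pill | Evening pill | Literal reply | Result | As intended? |
|---|---|---|---|---|
| taken | taken | yes | prompts stop | yes |
| missed | missed | no | follow-up shown | yes |
| taken | missed | yes | follow-up suppressed | no |
| missed | taken | no | needless follow-up | no |

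In the last row, three successive negative replies also lead to a question about why an evening pill was missed when it had been taken. The two wrong rows are those in which morning and evening status differ.

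**Day 1.** Only a PM reminder is scheduled, so a literal reply is no even if the evening pill was taken.

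**Timing line.** Reminders 2 and 3 each follow the previous one by 1 hour.

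- Read as *before* sleep time, the three prompts fall 2.5, 1.5 and 0.5 hours before it.
- Read as *after*, they fall 2.5, 3.5 and 4.5 hours after it. That conflicts with the EMA alert settings paragraph, where sleep and wake times are recorded so that the phone is less likely to ring during sleep.

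**The case against.** The strongest reply is that this is an editorial slip with no demonstrated consequence. The sentence just before the question names the evening pill and a PM time, and the prompt arrives in the evening. A wrong branch requires the participant to pass over that sentence and answer about the earlier dose. The documents also show only the protocol table, not the text programmed into the app. All of this stands, and it limits the point to a minor one. It does not remove the contradiction, because the question as written has a different truthful answer whenever the two doses differ.

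The Day 1 message, "Don't forget to take your Chantix pill tonight", also points to the intended dose, but on only 1 of the 89 PM days. On the other 88, Table 2's message mentions both doses, so the opening sentence and the column heading must carry the meaning.

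Three stronger readings are tempting, and the documents support none of them.

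- **That half of all evenings go wrong.** Two of four patterns is a statement about logic, not frequency. The plan gives no rate for days on which morning and evening status differ.
- **That the faulty question appears 89 × 3 = 267 times per participant.** This is a ceiling that needs negative replies to Reminders 1 and 2 on every PM day. Someone who always answers yes to Reminder 1 sees the item at most 89 times.
- **That the trial's outcome data are corrupted.** Abstinence is confirmed by expired CO. Adherence is collected in all arms by daily EMA and by questionnaire (Section C, Study Measures). Section D names no outcome built on reminder replies.

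The opposite overstatement, that nothing in the outcomes can be touched, also goes too far. Measurement is unaffected, but lost prompts could dilute the reminder effect that Aim 2 tests.

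The timing line is largely resolved by context, as the working shows, and adds little weight. It still has to be stated one way before it can be programmed reliably.

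**Conclusion.** The point holds as a minor internal contradiction. Confidence is high for the wording and the branching, but not for any effect on participants. The item is scheduled on up to 89 of 91 treatment days in the two reminder groups, assuming full treatment and reminders left on.

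The consequences are possible loss or needless repetition of evening follow-up prompts, and evening replies and reasons that may not refer to the evening pill. The first evening prompt still appears with a correct opening sentence. The share of participants who answer literally, and so any weakening of the reminder intervention, cannot be estimated from the documents. The conclusion assumes that the app follows Table 2, which the documents do not confirm.

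**What to change.** 1. In PM Reminders 1, 2 and 3 of Table 2, change *this morning* to *this evening*, in line with their opening sentence and the PM reason item.
2. Reconcile the timing of PM Reminder 1 into one unambiguous offset, consistent with the sleep-time settings described under EMA alert settings.
3. Check the text and timing programmed in the app against the amended table.
4. If the faulty wording was deployed, record this and flag the evening reminder replies and reasons as unreliable.

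The cost is three cell edits, one timing line and a check of the app. Sample size, visits, randomization and dosing are unchanged.

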**Table 3. NRT reminders**

1. Don't forget to use nicotine gum/lozenges regularly throughout the day! It is recommended that you use a piece of gum/lozenge every 1-2 hour.
 
After you have been smoke free for 6 weeks, taper down to using a piece of gum/lozenge every 2-4 hours and then after being smoke free for 8 weeks, taper down to a piece every 4-8 hours.
	
2.	Have you used a piece of gum/lozenge within the past 2 hours?  No Yes
3.	(If 2 = No) Have you used a piece of gum/lozenge within the past 4 hours?  No Yes
4.	(If 3 = No) Have you used a piece of gum/lozenge within the past 8 hours?  No Yes

**Table 4. Study compensation schedule (all groups)**

Visit	Weeks Post-Quit	Questionnaires	Smartphone Assessments	Total Per Week
1	-1	\$20		\$20
2	0	\$20	up to \$10	\$30
-	1	-	up to \$10	\$10
-	2	-	up to \$10	\$10
-	3	-	up to \$10	\$10
3	4	\$20	up to \$10	\$30
	5	-	up to \$10	\$10
	6	-	up to \$10	\$10
	7	-	up to \$10	\$10
4	8	\$20	up to \$10	\$30
	9	-	up to \$10	\$10
	10	-	up to \$10	\$10
	11	-	up to \$10	\$10
5	12	\$20	up to \$10	\$30
6	26	\$20	-	\$20
Total Possible				up to \$250

**Figure 1: Study Timeline**

Developing a Quit Plan. At baseline, eligible participants will meet with a tobacco cessation counselor who will provide an overview of the tobacco cessation program, and help participants to set and prepare for their quit date. Participants will be asked to quit smoking the evening prior to their next weekly appointment (Visit 2).

Counseling. Participants will complete counseling session in-person or remotely with a Tobacco Treatment Specialist at the baseline visit and each visit through 4 Weeks Post-Quit. The counselor will check in with participants about the difficulties and successes they have experienced, and plan for any challenging situations that are anticipated. Advice and support will be provided as needed. Topics will include 1) the impact of tobacco on health/benefits of quitting, 2) stress management strategies, 3) making positive lifestyle changes, 4) developing

coping skills, and 5) relapse prevention. The counselor will check in with participants each week about the difficulties and successes they have experienced, and plan for any challenging situations that are anticipated.

Compensation. Participants will receive a \$20 payment for completion of the Baseline visit, Quit Day, 4 Weeks Post-Quit, 8 Weeks Post-Quit, 12 Weeks Post-Quit, and 26 Weeks Post-Quit. (see Table 4 for study compensation schedule). In addition, participants will receive up to \$10 weekly for completing the daily smartphone assessments. Specifically, they will receive \$10 for completing at least 6 out of 7 EMAs, and \$5 for completing at least 4 out of 7 EMAs each week. Participants who complete 3 or fewer EMAs will not receive additional compensation. Participants may earn up to \$250 for participation in the study.

Discontinuing Reminders, Varenicline, or NRT. Using the following guidelines a participant may continue in the study if: 1) they no longer wants to receive reminders via the app, we will disable app reminders, 2) they no longer wants to take varenicline, we will have them delete the app, but will still ask that they come in to the clinic for in-person visits for follow-up, 3) they no longer wants to take NRT, they will be asked to answer that they didn't chew gum on the EMAs.

Remote Treatment Follow-up Visits. Due to the evolving circumstances regarding COVID-19, participants may complete any follow-up visits remotely. The requirements and compensation for remote visits will be identical to in-person visits. Participants will remotely complete web-based questionnaires and provide a smartphone-based CO measurement using a Bedfont iCO smokerlyzer. Participants may also keep the study smartphone until the 26 Weeks Post-Quit visit if necessary.

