**Abstract:** Varenicline is considered to be a first-line tobacco cessation treatment. Previous studies have evaluated the impact of the combination of varenicline and nicotine patches (versus varenicline alone) on smoking cessation, though findings have been equivocal. **No studies to date have evaluated the combination of varenicline and oral nicotine replacement therapy** (NRT; i.e., nicotine lozenges or gum). Nicotine lozenges and gum can provide acute relief during cravings and high risk situations, which offers individuals the flexibility to deliver nicotine when they need it most (in contrast with the continuous and passive delivery of nicotine offered via the patch). Prospective clinical trials are needed in real-world settings to determine whether the combination of varenicline and oral nicotine replacement therapy (i.e., lozenges, gum) is superior to varenicline alone for smoking cessation. The proposed *pilot* randomized trial would enroll 100 participants over 1 year ( $\approx$ 8 participants per month) utilizing a 2x2 factorial design. Twelve weeks of a pharmacological intervention [varenicline + oral NRT (VAR+N) vs. varenicline alone (VAR)] will be crossed with automated medication reminders (reminder messages vs. no reminder messages). All participants will receive an adapted version of the standard counseling offered through the Tobacco Treatment Research Program (TTRP). The primary outcomes will be biochemically-verified smoking cessation at 12 and 26 weeks following a scheduled quit attempt (1 week after enrollment). Smartphone-based ecological momentary assessment (EMA) will be employed to measure withdrawal symptoms, medication adherence, side effects, and adverse events using the Insight™ platform developed by the Stephenson Cancer Center (SCC) mHealth Shared Resource. This pilot study will provide information regarding the feasibility, acceptability, and preliminary efficacy of combination varenicline and oral NRT for smoking cessation, which will support an NIH funding application

for a larger, adequately powered study.

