### **C. Research Design and Methods**

**Study Design.** The study will utilize a **2x2 factorial design** in which participants are randomized to pharmacological treatment (VAR+N or VAR) and medication reminders (reminders or no reminders) at baseline (see Table 1). All participants will receive 12 weeks of varenicline after the standard 1-week titration period, with half of participants additionally receiving oral NRT (gum or lozenges, based on participant preference). Those assigned to VAR+N with medication reminders will receive smartphone prompts at scheduled intervals (during waking hours) with a reminder to use oral NRT regularly and as directed. The primary study outcomes will be carbon monoxide (CO)-confirmed 7-day point prevalence abstinence at 12 and 26 weeks post-quit date.

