### **Study Measures.**

Screening Measures (online or over the phone). Screening data will be collected using the secure web-based REDCap platform, which provides an intuitive user interface that streamlines project development and improves data entry through real-time validation rules. The initial online screening will include assessment of demographics, smoking history, readiness to quit, and other eligibility criteria.

Traditional Questionnaire Measures. Questionnaire data, including measures of tobacco/health history, sociodemographic characteristics, nicotine dependence, withdrawal symptom severity, depression, perceived stress, mental health, beliefs about medications, medication adherence, and self-efficacy will be collected via REDcap on tablet computers. The amount of time needed for participants to complete the computer-administered questionnaires varies by study visit. It is estimated that the longest visit (baseline) will require one hour to complete. We have found that even individuals with no experience using computers have had few problems completing study assessments. The questionnaire appendix will come from the TTRP IRB 6951.

Biological/Anthropometric Measures. Expired CO levels will be measured at each visit either in-person using the portable Vitalograph ecolyzer or remotely using the Bedfont iCO smokerlyzer which will interface the Insight™ smartphone application. Please note that the Insight™ smartphone application has integrated automated and secure (i.e., encrypted) facial recognition software to ensure that only the participant provides a CO breath sample. Self-reported abstinence from smoking will be verified with a CO level of ≤ 6 ppm at all subsequent post-quit visits. Body Mass Index (BMI) will be calculated (kg/m^2) based on height and weight measurements collected at the baseline visit.

**Ecological Momentary Assessment (EMA).** EMA can accurately measure phenomena in real-time, natural settings. EMA items will identify fluctuations in key variables that predict study outcomes with less bias than traditional in-person assessments.

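### Participants who stop varenicline are told to delete the app that the remote CO test and its identity check run through, so they have no described remote route to the CO-confirmed primary outcome

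*Combined protocol and SAP*

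**What the plan says.** All of the following is in section C of the combined protocol and SAP.

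- **Study Design** defines the primary outcome as "carbon monoxide (CO)-confirmed 7-day point prevalence abstinence at 12 and 26 weeks post-quit date".
- **Biological/Anthropometric Measures** sets the verification rule: "Self-reported abstinence from smoking will be verified with a CO level of ≤ 6 ppm at all subsequent post-quit visits". CO is read in person on the Vitalograph device or "remotely using the Bedfont iCO smokerlyzer which will interface the Insight™ smartphone application". The app also carries "facial recognition software to ensure that only the participant provides a CO breath sample".
- **Remote Treatment Follow-up Visits** says that "participants may complete any follow-up visits remotely" and that at these visits they will "provide a smartphone-based CO measurement using a Bedfont iCO smokerlyzer". It makes no exception for anyone who has stopped varenicline. It also lets participants keep a study phone until the 26-week visit if needed.
- **Discontinuing Reminders, Varenicline, or NRT** has three guidelines. Someone who no longer wants reminders has them disabled. Someone who no longer wants NRT keeps answering the EMAs. For someone who no longer wants varenicline, "we will have them delete the app, but will still ask that they come in to the clinic for in-person visits for follow-up".

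Section D (Statistical Methods) gives no rule for a participant who reports abstinence but has no CO reading.

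**The concern.** The discontinuation guideline treats the app as a tool for daily assessment and reminders, which a person off varenicline no longer needs. The measures section also makes the app the instrument for remote verification of the primary outcome. Deleting it removes both.

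The consequence is selective. A participant who reports smoking needs no CO reading to be classified. Only a participant who reports abstinence needs one. So the people exposed are those who stopped varenicline, report that they have quit, and do not attend in person. Their outcome becomes missing or, if the analyst so decides, smoking.

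Stopping varenicline happens after randomization and may be related to the assigned treatment. The Specific Aims give reasons to take this seriously for both factors. Aim 2 hypothesizes better adherence with reminders. Aim 3 allows for more side effects, but also for milder withdrawal, in the combination arm. A rule that changes how the endpoint can be measured after such an event can distort either factorial contrast, and section D contains nothing that would repair it.

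**Working it through.** **Step 1: the rules side by side**

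| Question | Still on varenicline | Stopped varenicline |
|---|---|---|
| Remote visit allowed? | Yes | Yes under the remote-visit paragraph; asked to attend in person under the discontinuation paragraph |
| Remote questionnaires? | Yes (REDCap or telephone) | Yes, the same; Insight is not needed |
| In-person CO? | Yes | Yes |
| Remote CO with identity check? | Yes, through Insight | No described route once Insight is deleted |

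No app-free remote CO method, alternative identity check or reinstallation step is described. Reinstallation is not forbidden either. The gap is therefore confined to remote CO verification.

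**Step 2: timing.** Daily EMAs run for 13 weeks from baseline, which ends at week 12 post-quit. The second primary time point, week 26, is 14 weeks later (26 − 12 = 14). A remote CO reading at week 26 already needs the app after daily assessment has ended, so the CO function has a purpose separate from EMA and medication.

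**Step 3: is there a figure to reproduce?** No. The plan "would enroll 100 participants over 1 year", which is 100 / 2 = 50 per drug arm, and likewise per reminder group, if allocation is equal. It gives no abstinence, dropout or varenicline-stopping rates and no power calculation.

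**Step 4: illustration on assumed inputs.** Let *s* be the share stopping varenicline, *q* the share of stoppers truly abstinent, and *r* the share of those followed remotely who lose verification. None of these comes from the documents.

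Verified quitters lost per arm = 50 × *s* × *q* × *r*:
- low: 50 × 0.10 × 0.10 × 0.25 = 0.125, about 0.1
- high: 50 × 0.30 × 0.30 × 1.00 = 4.5

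If unverified cases are counted as smoking (also an assumption), and *q* and *r* are equal in the two arms, the shift in the risk difference is −(*s*₁ − *s*₀) × *q* × *r*:
- equal stopping: 0 in the null case
- 30% vs 10%, low: −(0.30 − 0.10) × 0.10 × 0.25 = −0.005
- 30% vs 10%, high: −(0.30 − 0.10) × 0.30 × 1.00 = −0.06

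If the arm with more stopping is the other one, the signs reverse.

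**Step 5: what a shift of that size could do.** Assume 30% vs 45% abstinence, 50 per arm, and a two-sided test at Aim 1's threshold of 0.2. Power is 0.61 with no shift, 0.49 if 3 points are lost from the better arm, and 0.37 if 6 points are lost. This is for scale only. The planned model is a logistic regression with an interaction and covariates, and Aim 1 does not say whether its p-value is one- or two-sided.

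**The case against.** The strongest reply is that this is a wording gap with a small affected group. The discontinuation guideline exists to keep stoppers in follow-up, not to drop them. In-person CO stays open to all of them. Section B says the treatment program in which the study runs can arrange transport to key visits for participants with transportation difficulties in the Oklahoma City metro area. Remote enrollment does not imply that a person cannot travel. Staff could also reinstall the app for a single reading. All of this stands, and it limits the size of the problem. It does not supply a described remote route, and an unwritten workaround may be applied unevenly.

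Some stronger readings are tempting but not supported:

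- **Follow-up of stoppers is restricted to the clinic.** The guideline asks them to attend; it does not bar remote visits, and the remote-visit paragraph covers all participants.
- **Only those who complete treatment may keep the study phone.** The remote-visit paragraph draws no such line, and nothing asks stoppers to return a phone or CO device.
- **The result is a known bias against the combination arm.** Aim 3 says only that side effects may be more frequent there, and also hypothesizes milder withdrawal. A participant with side effects might stop the NRT instead, in which case the app stays.
- **One lost quitter would reverse the Aim 1 decision.** An unadjusted two-sided z test gives p = 0.198 for 19/50 vs 13/50 and p = 0.280 for 18/50 vs 13/50. One-sided, the second is 0.280 / 2 = 0.14, still under 0.2. Sensitivity near a cutoff is common to all small trials, and this is not the planned analysis.

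**Conclusion.** The point holds as an unreconciled conflict between three paragraphs of section C. Followed as written, participants who stop varenicline have no described remote route to an identity-verified CO reading for the primary outcome, so ascertainment depends on an event after randomization. This goes beyond missing detail, because a stated instruction removes the measuring instrument.

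The effect on the Aim 1 and Aim 2 contrasts is conditional. It needs stopping, abstinence among stoppers, or reliance on remote visits to differ between groups. The documents do not allow its direction or size to be determined. The shift of 0.5 to 6 percentage points rests entirely on assumed rates and on counting unverified cases as smoking, a rule the plan does not state. The point merits correction mainly because the correction is cheap.

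**What to change.** In the varenicline item of the discontinuation paragraph, replace deletion of the app and the request for clinic attendance with wording such as:

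> If a participant stops varenicline, the EMA and medication prompts are switched off. The Insight CO function and face check stay installed, and any iCO device or study phone issued is kept, until the 26-week visit. Follow-up visits may be in person or remote, whether or not varenicline is continued.

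Add a cross-reference to the remote-visit paragraph so that the two agree. No change is needed for those who stop NRT or reminders, because their app is not removed. The change concerns outcome measurement only and alters no dose or treatment rule.

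The cost is a wording amendment, a prompts-off setting in the app, and a few devices or phones staying with stoppers until week 26. The protocol already lets study phones be kept that long where necessary.
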